4.3.3 End of Study

Protocol mandated monitoring of oxygen saturations will continue until the child reaches 6 months corrected age. At that time, if the child remains in supplemental oxygen, decisions about subsequent monitoring will be made by the child's pulmonologist.

If the infant is at home in room air without intermittent hypoxemia (definition below) for 8 continuous weeks, study monitoring may be discontinued at parental request (earliest possible discontinuation of study monitoring at 48 weeks PMA) before 6 months corrected age. All study data will still be collected at 3 and 6 months CA.

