The PI will be responsible for monitoring the data and safety of all participants. All study procedures will receive IRB approval prior to recruitment or enrollment of participants. In addition to the data management procedures outlined above, the PI will hold monthly study team meetings to evaluate the safety and progress of all research procedures. Standard procedures for all data collection methods will be reviewed at the start and periodically throughout the study. Data checks for errors will be performed prior to analysis. Adverse events and serious adverse events will be reported to the

TABLE 1: SCHEDULE OF STUDY PROCEDURES

Study Activity	Recruitment Phase & Screening	Enrollment Phase	Study Timeframe					
			Baseline 34-44 (weeks)	Discharge	Weekly after discharge	Monthly after discharge	3 Months CA	6 Months CA
Pre-Enrollment Pool EPIC-CHOP/PENN/PAH	X							
Medical Record Review	X							
Conduct Eligibility Screen	X							
Approach Families (Beginning 34weeks, PMA)		X						
Parental Consent			X					
Participant Randomization			X					
Weight, length, and head circumference are measured			X				X	X
Placement of SPO2 study monitors/ training with families					Continuous over 6 months			
Feeding questionnaire and diary							X	X
Data from monitor are reviewed by study team and family is contacted if needed					Weekly data transfers to CHOP			
Feeding Questionnaire**							X	X
ITQOL-SF47 (Parent/Child quality of life) **							X	X
Health care utilization data is collected							X	X
Bayley Scales of Infant Development Screener								X
Participant Compensation. Payments issued monthly(\$50/visit; up to 6 visits)						X		

Adverse Event/Serious Adverse Event Assessment			X	X	X		X	X
--	--	--	---	---	---	--	---	---

FIGURE 1: SCHEMATIC OF STUDY PROCEDURES

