3.1.4 Phase 3 – 3 and 6 month corrected age outcomes assessment

Per standard of care, participants will be evaluated in the CHOP Neonatal Follow-up Program at 3 and 6 months corrected ages. Several study outcomes, clinical outcomes in particular, will be assessed during these clinical visits. Based on the limited existing literature, average age of weaning from supplemental oxygen in infants with BPD is between 2-4.5 months corrected age.(9,10) For the current study, the oxygen titration protocol and study oximetry will continue until 6 months corrected age, with the expectation that nearly all participants will have weaned to room air by the end of the study period. If participants remain on oxygen after the conclusion of the study, the pediatric pulmonologist primarily responsible for the child's ongoing BPD care will make decisions about further weaning. For all other participants, ongoing clinical care will be provided by the neonatal follow-up clinic and pediatrician.

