5.1.4 Outpatient Data Collection

During the remainder of the study period, the following data will be collected:

- Rehospitalizations: location, duration, and ICU care, primary reason for hospitalization
- Medication use
- Visits to doctor or emergency room, with reason
- Procedures or surgeries
- Growth parameters as assessed at any clinical visit(s)
- Mode of feeding
- Developmental assessment (Bayley screener)

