5.2 Efficacy Evaluations

5.2.1 Efficacy Evaluations: Oximetry

This pilot trial is designed to assess the efficacy of continuous transmission of pulse oximetry from the home environment, for use in oxygen titration and monitoring for clinical care and research purposes. Therefore the study outcomes are designed to assess the efficacy of the study monitoring itself as well as the intervention of randomization to higher or lower oxygen saturation target ranges for infants with BPD.

For this study, we define intermittent hypoxemia as $\text{SpO}_2 < 80\%$ for > 30 seconds. In keeping with the prior literature, we will also report severe IH events, defined as $\text{SpO}_2 < 80\%$ for > 60 seconds. In the current study, we will utilize 2-second sampling and averaging times. IH will be measured longitudinally throughout the study period in all participants regardless of home oxygen use. IH will be reported as weekly average number of events per “night” based on 8 hours of recorded oximetry data per night. If data are not available for all nights in a week, the available data will be used to estimate average number of events per night for that week. Specific outcomes of interest are differences between the two groups in incidence of IH at 40 weeks PMA, 3 months CA, and 6 months CA. In addition, we will report percent of recording time spent $< 80\%$, $< 85\%$ and $< 90\%$ SpO_2 over the study period.

Duration of exposure to supplemental oxygen will be measured as the number of weeks between 36 weeks PMA (the time of formal diagnosis of BPD) and complete discontinuation of supplemental oxygen. This outcome is defined in weeks, not days, because this more closely matches the pace

with which changes are made in the outpatient setting. Prior studies demonstrated that it can be challenging, but nevertheless possible to keep infants in goal SpO₂ ranges during hospitalization. However, no studies have performed this maneuver after discharge. To demonstrate successful implementation of our study intervention and monitoring technology, percent of usable data and percent of time with SpO₂ in target range over time will be reported. Time with SpO₂ in the target range will be reported as a percent of oximeter recordings with SpO₂ in range, out of total recorded time. These outcomes are key components of demonstrating feasibility of the study intervention for future research and clinical use.

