6.3.2 Efficacy Analysis

The primary analysis will be based on an intention to treat approach and will include all randomized subjects. Interpretation and analysis of downloaded saturation data throughout the study will be managed in two ways. Saturation data will be cleaned, processed, and analyzed weekly. This will allow real-time assessments in order to ensure that the oximeter is being applied routinely and sufficient usable data are available. In addition, the data will be analyzed to determine whether the participant is having SpO₂ below the target range that would necessitate either increase in flow or medical attention.

Generalized estimating equations will be used for continuous primary outcomes such as frequency of IH and growth and logistic models for binary outcomes. Models will be adjusted for potential confounders that are significantly different in bivariate testing, because differences may exist despite randomization due to small sample size. Variables that will be considered for inclusion in the model are gender, gestational age, birth weight, race, small size for gestational age, and severity of BPD. The remaining exploratory outcomes will be compared between groups with simple bivariate tests such as t-tests and χ^2 tests. Exploratory subgroup analyses will be performed to evaluate the effect of the intervention on the gestational age and severity of BPD strata. Lastly, we will test for PMA week-specific differences between study groups through regression models controlling for key covariates, and using adjustments to account for multiple testing across PMA weeks. Given the sample size of this pilot study, we will likely not have sufficient power to draw definitive conclusions in these exploratory analyses; however, these approaches to the data are likely to be valuable in planning future studies.

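### Study oximetry may stop because an infant has been free of intermittent hypoxemia, and the plan does not clearly say how such infants enter the 3- and 6-month comparison

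*Combined protocol and SAP*

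**What the plan says.** The primary endpoints in section 6.1 are the incidence of IH and the total duration of hypoxia up to 6 months CA. Section 5.2.1 specifies the IH comparison as "differences between the two groups in incidence of IH at 40 weeks PMA, 3 months CA, and 6 months CA". It also asks for the percent of recording time below 80%, 85% and 90% SpO2 over the study period. All of this comes from the study oximeter.

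Section 4.3.3 lets that recording end early: once the infant has been at home "in room air without intermittent hypoxemia (definition below) for 8 continuous weeks, study monitoring may be discontinued at parental request". The earliest stop is 48 weeks PMA. The section then adds: "All study data will still be collected at 3 and 6 months CA".

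Table 1 shows the oximeter only as "Continuous over 6 months", not as a procedure at the 3- or 6-month visit. Section 5.1.4, the outpatient data list, has no oximetry item.

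The one rule for missing oximetry is in section 5.2.1: "If data are not available for all nights in a week, the available data will be used to estimate average number of events". It therefore fills in a week that has some recorded nights. For the analysis, section 6.3.2 takes all randomized infants by intention to treat and states: "Generalized estimating equations will be used for continuous primary outcomes such as frequency of IH and growth". It gives no rule for weeks with no recording after a permitted stop.

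**The concern.** The stop is conditional on the outcome (no IH) and on a state that treatment affects (off oxygen). If the analysis uses only what was recorded, the infants who leave the 6-month comparison are selected for low IH. Those who remain still have IH, are still on oxygen, or come from families who chose to continue.

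Three results are exposed:

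- **Level of IH at 6 months CA.** It would be overstated. Section 1.3 promises data on whether IH continues after discharge, and section 6.4 says no preliminary IH data exist, so the level matters for planning the next trial.
- **Arm contrast.** It is biased if stopping differs between arms.
- **Percent time over the whole study period.** An infant who stops contributes only the earlier weeks.

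Unweighted GEE is in general valid only when missingness does not depend on past outcomes. Here a permitted stop depends on them by rule.

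**Working it through.** **Timing.** Inputs: the 8-week run and 48-week limit (4.3.3), the comparison times (5.2.1), and 1 month = 365.25/12/7 = 4.348 weeks.

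- The plan's 48-week limit matches a clean run that starts at 40 weeks PMA: 40 + 8 = 48. The 40-week comparison is therefore unaffected.
- 3 months CA = 40 + 3 × 4.348 = 53.0 weeks PMA. To be missing there, the run must start by 53.0 - 8 = 45.0 weeks.
- 6 months CA = 40 + 6 × 4.348 = 66.1 weeks PMA. To be missing there, it must start by 66.1 - 8 = 58.1 weeks, which is 18.1/4.348 = 4.2 months CA.
- Section 3.1.4 says that "average age of weaning from supplemental oxygen in infants with BPD is between 2-4.5 months corrected age". If the clean run begins on the day of weaning, the stop opens at 48.7 + 8 = 56.7 weeks (weaned at 2 months) to 59.6 + 8 = 67.6 weeks (weaned at 4.5 months). That is 9.4 weeks before to 1.5 weeks after the 6-month point. Any later IH event restarts the run, so these are the earliest dates.

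Missing the 6-month point is thus possible over most of the cited weaning range. Missing the 3-month point is possible for few infants.

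**Level.** Let a share f stop and have no IH afterwards. Then recorded mean / true mean = 1/(1 - f), which is 1.00 at f = 0, 1.11 at 0.10 and 2.0 at 0.50.

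**Arm contrast, no true effect.** With stop shares fL (lower arm) and fH (higher arm), the observed higher-to-lower ratio is (1 - fL)/(1 - fH).

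| fL | fH | Ratio |
|---|---|---|
| 0.30 | 0.30 | 1.00 |
| 0.40 | 0.30 | 0.60/0.70 = 0.86 |
| 0.30 | 0.40 | 0.70/0.60 = 1.17 |

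With 21 infants per arm (42 split equally), either unequal case leaves 21 × (0.6 + 0.7) = 27 infants recorded.

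If stoppers keep a quarter of the others' IH rate, replace 1 - f by 1 - f + 0.25f. The 40/30 case becomes 0.70/0.775 = 0.90 and the reverse 0.775/0.70 = 1.11.

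**Zero events after a stop.** If stoppers truly have none, the zero-filled mean is (1 - f) × true/(1 - f), so the true value is recovered. If they keep a quarter, the 40/30 case gives 0.903 × 0.70/0.60 = 1.05 zero-filled, against 0.90 from recorded data. In this example the two analyses lie on either side of the true ratio of 1.

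**Percent time.** Suppose hypoxemia halves every 8 weeks (assumed; range 4 to 12). For an infant recorded over weeks 40 to 56.7 only, divide the mean of exp(-kt) over 16.7 weeks by its mean over 26.1 weeks. The result is 1.33 (1.49 at 4 weeks, 1.24 at 12) times the full-period value.

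All stop shares, the residual rate and the half-life are assumptions. The documents give none of them.

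**The case against.** **The plan may already cover it.** IH at 3 and 6 months CA is a named outcome, so the sentence promising continued data collection can be read to include oximetry. Section 5.1.4 lists no oximetry for any infant, so its silence proves little. This stands: the fault is ambiguity, not a clear decision to leave these infants unrecorded. But no recording is scheduled, and a clinic visit alone cannot supply a nightly average.

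**The stop may be rare.** It needs four things together: home, room air, 8 weeks without IH, and a parental request. Taken literally, that is no event in 32 nights (4 per week) to 56 nights. If events were Poisson, a rate of 0.1 per night gives only exp(-5.6) = 0.4% to exp(-3.2) = 4% of infants qualifying. Section 6.4 plans on 20 to 30 events per 8 hours at baseline. IH should fall with age and differs between infants, so this does not show that stops will be rare, but it leaves the frequency unknown.

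**Direction.** A reader might infer that the higher target will look better than it is. Table 2 asks more for a wean in the higher arm (at least 96% for over 95% of time, against above 94% for at least 90%). The trial cited in section 1.3 had a median 2.5 weeks to the end of oxygen with the standard target against 5.7 with the high one. But those infants were enrolled at 32 weeks and about half were off oxygen by 36 weeks, so the gap does not transfer to months after term. If the higher target does reduce IH, the IH-free condition favours more stopping in that arm. The net direction is unknown.

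**GEE.** With a linear model and a correct mean and covariance, bias from stopping on observed data can be small. That is fair, though less reassuring for skewed IH counts.

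**Existing checks.** Percent of usable data (5.2.1) and drop-out at the interim analyses (6.5) are reported, but neither counts early stops by arm.

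**Conclusion.** The concern holds in a limited form. Recording can end because the primary outcome was zero, and the plan neither clearly schedules later oximetry for these infants nor says how their empty weeks are analysed. A recorded-infants-only analysis would overstate mean IH at 6 months CA by 1/(1 - f) if stoppers have no IH, and would distort whole-period percent time. The 3-month comparison is exposed for few infants and the 40-week comparison for none.

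Bias in the arm ratio needs unequal stopping and can go either way: 0.86 or 1.17 for a 40%/30% split. Equal stopping leaves the ratio unchanged. A reader might set such figures against the 30% reduction used for sample size and conclude that stopping could produce a false finding. The documents do not support that, because they give no stop rates; the figures are illustrative and the bias could be near zero. The gap in the rules does not depend on those shares, and it is cheap to close.

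**What to change.** 1. In section 4.3.3, keep the parents' right to stop. State that the data still due at 3 and 6 months CA include oximetry, and ask families who stopped to record for one week at each time, using the existing minimum of 4 days of 8 hours. Make this a voluntary request.
2. In section 6.3.2, use the re-recorded week in the GEE. Where there is none, prespecify an analysis with zero IH events after a permitted stop, reported beside the available-data analysis. Weighted GEE should be optional only: with about 42 infants the weights rest on the few eligible families who go on recording, and are undefined if none do.
3. Report percent time below 80%, 85% and 90% in common windows at 40 weeks PMA, 3 months CA and 6 months CA, beside the whole-period value.
4. Report the number and PMA of early stops by arm.

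The cost is a short amendment with a consent sentence, up to two extra weeks of night recording for families who stopped, and oximeters kept or reissued for those weeks. Titration, visits and sample size do not change.

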4.4 Unscheduled Visits

It is likely that the participant will have interim clinical visits to the Neonatal Follow-up Program, Pulmonary clinic, and the pediatrician. Wherever possible, study visits will be arranged to align with these visits.

4.5 Concomitant Medication

The majority of infants at our center are discharged without caffeine therapy; clinicians will be encouraged to continue this practice because caffeine is likely to impact incidence of intermittent hypoxemia.(8) The study will not dictate diuretic use either in hospital or after discharge, but clinicians will be strongly encouraged to wean diuretics before oxygen.(11) Ultimately, however, this will be a clinical decision. Exposure to caffeine, diuretics, bronchodilators, steroids, and any other medications will be recorded throughout the study. The dates of administration, dosage, and reason for use will be included.

4.6 Subject Completion/Withdrawal

Subjects may withdraw from the study at any time without prejudice to their care. They may also be discontinued from the study at the discretion of the Investigator for lack of adherence or tolerance to testing procedures. Participants will not be withdrawn from the study for missing follow up appointments. If the Investigator becomes aware of any serious, related adverse events after the subject completes or withdraws from the study, they will be recorded in the source documents and on the CRF.

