3.3.2 Total Number of Study Sites/Total Number of Subjects Projected

Infants will be recruited from 3 neonatal intensive care units (NICUs): The Children's Hospital of Philadelphia (CHOP) NICU, the adjacent Hospital of the University of Pennsylvania (HUP) NICU, and Pennsylvania Hospital (PAH) NICU. All outpatient care will take place at CHOP. Up to 50 participants may be enrolled to reach our target sample of 42 patients with evaluable data.

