5.2.2 Efficacy Evaluations: Clinical

In this pilot study, physiologic (oximetry) data are the primary outcomes. All clinical outcomes/assessments of efficacy are exploratory and descriptive. Methods and timing of measures that will be used to assess efficacy are:

Primary Clinical Outcome:

Growth in kilograms between 36 weeks PMA and 6 months CA as well as other growth parameters.

- Change in Length (cm)
- Weight for length
- Head circumference (cm)

Secondary Clinical Outcomes:

- Feeding questionnaire: The questions that will be asked at 3 and 6 months are selected to assess feeding skills and estimate caloric intake. The questions are selected from longer questionnaires administered as part of the Millennium Birth Study, with permission from the author of the original study.(13)
- The ITQOL---SF47- Parent and child quality of life survey: The Infant Toddler Quality of Life Questionnaire™ (ITQOL) was developed for use in infants and toddlers at least 2 months of age up to 5 years. The Infant Toddler Quality of Life Questionnaire™ (ITQOL) adopts the World Health Organization's definition of health, as a state of complete physical, mental and social wellbeing and not merely the absence of disease. The survey was developed following a thorough review of the infant health literature and a review of developmental guidelines used by pediatricians. The ITQOL includes questions that assess the impact of health on both child and parent quality of life.
- Medical resource utilization recorded at 3 and 6 months corrected age: medications (including dose, route, frequency, and indication), doctor and emergency room visits, hospitalizations (whether or not in ICU, duration, and indication), therapies (type and frequency), and home equipment use. These data will be extracted from the EMR wherever possible and verified with the participant's parent(s).
- Development: Per standard of clinical care, the Bayley Scales of Infant Development- 3rd Edition Screening Test is administered to all children who attend the Neonatal Follow-up Program (NFP) at 6 months corrected age. (All children eligible for this study will be

followed at the NFP per standard of care) Results of this clinical evaluation will be recorded for the study.

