9.1.2 Blinding

The plan for allocation concealment is described above in section 3.2. Given the nature of the intervention to be evaluated participants and research staff will not be blinded to group assignment.

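### Section 4.6 lets an unblinded investigator end an infant's study participation for poor adherence to testing, with no provision to keep collecting outcomes; the rule in 4.3.3 should be extended to cover these infants

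*Combined protocol and SAP*

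**What the plan says.** Section 4.6 gives the investigator a power of removal: "They may also be discontinued from the study at the discretion of the Investigator for lack of adherence or tolerance to testing procedures". It sets no threshold of non-use and no number of contact attempts. It limits the power in one respect: "Participants will not be withdrawn from the study for missing follow up appointments". It then covers one kind of later information: "If the Investigator becomes aware of any serious, related adverse events after the subject completes or withdraws from the study", the event is recorded. It mentions no other data after exit. Section 9.1.2 confirms that "participants and research staff will not be blinded to group assignment".

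Section 4.6.1 deals with families who withdraw. Those who want collection and use of their health information to end are asked to tell the team. Despite its title, the section lists no assessment.

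Section 4.3.3 handles another exit. A parent may ask to stop study monitoring once the infant has been at home, breathing room air and free of intermittent hypoxemia (IH), for eight weeks running. For these infants, "All study data will still be collected at 3 and 6 months CA".

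On analysis, section 6.3.2 states: "The primary analysis will be based on an intention to treat approach and will include all randomized subjects". Section 6.3.3 puts every subject entered into the safety analysis. No method for missing data is given.

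**The concern.** Stopping a measurement device and leaving a randomized trial are different events. The protocol separates them in 4.3.3 but not in 4.6. An infant whose family cannot keep the probe on may lose the whole of follow-up, although most clinical outcomes do not depend on the probe.

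The removal happens after randomization, is discretionary, and is decided by someone who knows the allocation. Adherence could also differ by arm. In the earlier trial of infants oxygen-dependent at 32 weeks, cited in section 1.3, median time on the intervention until oxygen stopped was 2.5 weeks in the standard-target group and 5.7 weeks in the high-target group. Under section 7.1, infants sent home on oxygen also receive a clinical monitor. The burden of monitoring, and its perceived value, may therefore depend on the assigned target.

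Removal for poor tolerance raises a further problem. Section 5.3 names harm to parental quality of life as a potential adverse outcome, and 9.4.2 accepts that alarms may bother families. Families in whom that harm occurs may be among those removed.

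**Working it through.** The point rests on the text. The arithmetic at the end only shows scale.

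**Step 1: the two exits compared.**

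| | Section 4.3.3 | Section 4.6 |
|---|---|---|
| Trigger | Room air, no IH for 8 weeks | Poor adherence to, or tolerance of, testing |
| Initiated by | Parent | Investigator, unblinded |
| What ends | Study monitoring | Participation in the study |
| 3- and 6-month data | Kept, expressly | Not mentioned |
| Later safety data | Within the 3- and 6-month data | Serious, related events that come to the investigator's notice |

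**Step 2: what the analyses need.** Section 6.3.2 needs outcomes on all randomized infants, and it names growth beside IH frequency as a primary continuous outcome for the estimating-equation models. Section 6.2 defines safety as differences in growth, re-hospitalizations and any safety events at 3 and 6 months. That is much wider than serious, related events. An infant removed under 4.6 stays in the denominator but may contribute no later data.

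**Step 3: what could still be collected without the oximeter.**
- Section 3.1.4: Neonatal Follow-up Program (NFP) visits at 3 and 6 months are standard care.
- Section 5.1.4: growth is taken from any clinical visit; re-hospitalizations and other visits are recorded.
- Section 5.2.2: utilization comes from the medical record where possible and is checked with parents. The Bayley screener is part of the NFP visit, and all eligible children are to be "followed at the NFP per standard of care".
- Feeding and quality-of-life questionnaires need the parents' cooperation.

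**Step 4: scale, on assumptions.** Section 6.4 claims more than 80% power for a 0.5 kg growth difference with 42 infants. It gives no SD or alpha, so the claim cannot be reproduced. Assuming two-sided alpha 0.05, 21 per arm and a normal approximation, the largest SD giving 80% power is

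SD = 0.5 / [(1.96 + 0.842) × √(2/21)] = 0.578 kg.

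Now assume no true effect, 25 infants per arm, and k removed from one arm only, whose mean growth is g SDs below that of the infants kept.

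- Shift in that arm's mean = g × k/25 SD.
- Standard error of the difference = √[1/25 + 1/(25 − k)] SD.
- False-positive probability = chance that |Z| > 1.96 when Z is centred at shift ÷ standard error.

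| k | g | Shift (SD) | Shift (kg) | False-positive probability |
|---|---|---|---|---|
| 4 | 0.5 | 0.08 | 0.046 | 5.8% |
| 4 | 1.0 | 0.16 | 0.092 | 8.4% |
| 8 | 0.5 | 0.16 | 0.092 | 8.0% |
| 8 | 1.0 | 0.32 | 0.185 | 17.5% |

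Eight is the gap between the enrolment ceiling of 50 and the target of 42 (8/50 = 16%). If the removed infants grew better than the rest, the shift changes sign. If removals were balanced across arms on prognosis, the comparison would be little affected.

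**The case against.** The strongest reply is that 4.6 never says data collection stops. It is permissive, non-using families are contacted first (7.1.1), and missed appointments are not a ground for withdrawal. Section 4.6.1 implies that records may be used unless a family objects. This stands in part: the loss of follow-up is inferred from the wording on leaving the study and from silence. But 4.6.1 speaks of subjects who withdraw, not those the investigator discontinues, so it does not close the gap.

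A second reply is that the consequences are limited. A family that does not use the probe supplies no oximetry either way, so no IH data are saved. Sections 5.2.2 and 6.2 also call the clinical outcomes exploratory. The first half is right. The second is weakened by 6.3.2, which models growth as a primary outcome, and by the all-subjects safety analysis.

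A reader might also infer more than the text supports:
- **Retention depends on health.** Section 4.6 conditions removal on adherence or tolerance only. An ill infant whose family adheres keeps follow-up.
- **Infants who are well keep full follow-up.** Under 4.3.3 nightly oximetry stops, so later IH data may be missing for them too.
- **Dropped infants are replaced by adherent ones.** Section 3.3.2 says "Up to 50 participants may be enrolled to reach our target sample of 42 patients with evaluable data". That is a ceiling and a target, not a replacement rule, and enrolling more infants takes nobody out of the intention-to-treat set.
- **Data already collected on these infants are deleted.** Section 9.2 provides for deletion for individuals who withdraw. Whether that includes investigator discontinuation is unclear.

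**Conclusion.** The conflict is real. Section 4.6 allows discretionary, unblinded removal from the study for non-adherence and makes no provision for continued outcome collection, whereas 6.3.2 and 6.3.3 promise analyses of everyone randomized or entered. The data at risk are growth, utilization, development and non-serious or unrelated safety events, not the oximetry endpoints.

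Neither the size nor the direction of any bias can be found from the documents. It is tempting to claim a definite bias in growth against one arm, but the text does not support it. If families lose interest because the infant has done well and reached room air, those removed need not be the poor growers. The shifts of 0.046 to 0.185 kg rest on assumed numbers removed, one-arm removal, an assumed growth gap and an SD back-calculated from the power claim. What can be said without assumptions is that, with a target of 42, each infant lost is 1/42 = 2.4% of the sample. This is a cheap improvement, not a defect that invalidates the design.

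**What to change.** - In 4.6, state that non-adherence to, or intolerance of, study oximetry is not a ground for ending outcome follow-up.
- Apply the 4.3.3 sentence on 3- and 6-month data to every infant who stops study monitoring for any reason, unless the parent withdraws permission.
- Record the date, reason and decision-maker for each such stop, and report them by arm.
- Leave the oxygen titration rules unchanged. The sponsor should reconcile 4.6, 4.6.1 and 4.3.3 on how those rules apply to infants who stop monitoring.

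The cost is protocol wording, any matching consent text, and some extra chart review. Because the 3- and 6-month NFP visits are standard care, few extra contacts should be needed. An occasional visit may have to be arranged, as 4.3.2 already foresees at 3 months. Questionnaires will stay incomplete for a few families, and missing IH data will not be recovered.
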